3.3.2. Secondary Outcome Measures

3.3.2.1. Exacerbations and Healthcare Utilisation

- Time from randomisation to next hospital readmission or death due to a respiratory cause
- Total number of hospital readmissions all cause up to 48 weeks
- Total number of moderate exacerbations up to 48 weeks
- Time from randomisation to treatment failure (defined as the composite of three endpoints: 1. treatment intensification with systemic corticosteroids and/or antibiotics for respiratory reasons; 2. step-up in hospital care for respiratory reasons including transfer to the intensive care unit or readmission; or 3. all-cause mortality)
- Time from randomisation to death (all cause)
- Time from randomisation to death (respiratory cause)
- Time from randomisation to next hospital readmission (all cause)
- Time from randomisation to next hospital readmission (respiratory cause)
- Time to discharge from randomisation

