3.5 Table of endpoints/outcomes

Objectives	Outcome Measures	Timepoint(s) of evaluation of this outcome measure (if applicable)
Primary Objective	Time from randomisation to next hospital readmission or death (all cause)	Time to event between randomisation and first event, up to 48 weeks.
Secondary Objectives Exacerbation and healthcare usage	Time from randomisation to first hospital readmission or death (respiratory cause)	Time to event, up to 48 weeks.
	Total number of hospital readmissions (all cause)	48 weeks (minimum duration of trial treatment of 24 weeks)
	Total number of moderate exacerbations	48 weeks (minimum duration of trial treatment of 24 weeks)
	Time from randomisation to treatment failure	Time to event, up to 48 weeks.
	Time from randomisation to death (all cause)	Time to event, up to 48 weeks.
	Time from randomisation to death (respiratory cause)	Time to event, up to 48 weeks.
	Time from randomisation to first hospital readmission (all cause)	Time to event, up to 48 weeks.
	Time from randomisation to first hospital readmission (respiratory)	Time to event, up to 48 weeks.
	Time to discharge from randomisation	Time from randomisation to discharge, up to 48 weeks.
Quality of Life/Symptoms	Extended MRC dyspnoea score (eMRC)	Weeks 0, 4, 8, 12, 24, 36, 48* *See section 4.1 – Truncated follow-up; Patients randomised from July 2023 will receive minimum 24 weeks follow-up.
	St George's Respiratory Questionnaire (SGRQ)	
	COPD Assessment Tool (CAT)	
	Warwick-Edinburgh Mental wellbeing score (WEMWBS)	
	London Chest Activities of Daily Living Questionnaire (LCADL)	
Physiological Measures	Short physical performance battery (SPPB)	Weeks 0, 4, 8, 12, 24, 36, 48* *See section 4.1 – Truncated follow-up; Patients randomised from July 2023 will receive minimum 24 weeks follow-up.
	Handgrip Strength	

Inflammatory Markers	Serum eosinophil count	Weeks 0, 4, 8, 12, 24, 36, 48*
	Sputum eosinophil count	*See section 4.1 – Truncated follow-up; Patients randomised from July 2023 will receive minimum 24 weeks follow-up.
Safety and Tolerability	AE event rate per year in the 48 weeks of the trial from first dose	48 weeks*
	SAE event rate per year in the 48 weeks of the trial from first dose	*See section 4.1 – Truncated follow-up; Patients randomised from July 2023 will receive minimum 24 weeks follow-up.
	Clinical assessments and investigations	

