7.2 Informed Consent

Written versions of the participant information sheet and consent form will be presented to participants detailing the exact nature of the trial: what it will involve for the participant; the implication and constraints of the protocol; the potential side effects and any risks involved in taking part. It will be clearly stated that the participant is free to withdraw from the trial at any time for any reason, without prejudice to future care, and with no obligation to give the reason for withdrawal.

Due to the nature of the study (acute illness resulting in hospitalisation), the participant can be consented at any point within their inpatient stay, or within one week of discharge. Participants will be given time to consider the information and have the opportunity to question the researcher, or other independent parties, to decide whether they will participate in the trial. Written informed consent will then be obtained by means of participant dated signature and dated signature of the person who presented and obtained the informed consent, which will contain information that conforms to current data sharing and handling requirements.

The process for obtaining informed consent will be in accordance with the REC guidance, and GCP and any other applicable regulatory requirements, which may be introduced. Trial procedures including baseline assessments will not be undertaken until the informed consent form has been signed and dated by the participant. Should there be any subsequent amendment to the final protocol, which might affect their participation in the trial, then these will be discussed with the participant and, if applicable, continuing consent will be obtained using an amended consent form.

The original signed consent form will be retained at the study site within the Investigator Site File (ISF). One copy will be given to the participant, and a second copy retained in their medical notes.

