10.3.3 Secondary outcome analysis

All secondary end-points will be analysed using the ITT population, with the exception of adverse events, for which we will analyse the safety population, consisting of all participants who received at least one dose of trial medication. The count outcomes, number of hospital readmissions and number of moderate exacerbations over 48 weeks, will be analysed using the per protocol (PP) population where patients will be included in the analysis if they have a received a minimum duration of trial treatment of 24 weeks.

All time to event secondary outcomes will be analysed the same way as the primary outcome.

All count secondary outcomes, number of hospital readmissions and number of moderate exacerbations, will be analysed using a negative binomial regression model. If there is no evidence of over-dispersion, a Poisson regression model will be used in place.

All binary secondary outcomes will be compared between treatment groups using logistic regression.

All continuous longitudinal outcomes (repeated measurements) will be compared using mixed effects model with patient as a random effect to account for repeated measures over time. This method will enable handling of missing data within the follow-up visits.

This trial has a single primary outcome, therefore there will not be a formal adjustment for multiple significance testing.

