The time from randomisation to next hospital readmission (respiratory cause) is defined as a time to event outcome measured in days. The date of randomisation and the date of next hospital readmission (respiratory cause) will be used to calculate time to event. Where hospital readmission for respiratory cause doesn't occur during follow-up, time will be measured until the participant's last known follow-up assessment. A variable to indicate event (with a value of 1) or no event (with a value of 0) will be derived.

- Time to discharge from index admission

Time to discharge from index admission is a continuous outcome defined as the time (measured in days) from index admission to discharge. The date of index admission and the date of hospital discharge will be used to calculate length in days and the resulting index admission duration, expressed in days, will be incorporated into the baseline characteristics for analysis and reporting. Participants with a date of death and no discharge date will not have a value for length of index admission and therefore not included in the analysis of this outcome measure.

Quality of Life/Symptoms (Weeks 0, 4, 8, 12, 24, 36, 48*)

*See section 1.2 – Truncated follow-up; Participants randomised from June 2023 will receive minimum 24 weeks follow-up.

- Breathlessness:
 - Extended MRC dyspnoea score (eMRC)

The extended MRC dyspnoea scale is defined as an ordinal outcome. It consists of five statements about a perceived grade of breathlessness related to activity, with the grades defined as shown below:

- Grade 1: Breathless only with strenuous exercise.
- Grade 2: Breathless when hurrying on the level or walking up a slight hill.
- Grade 3: Walks slower than peers or stops when walking on the flat at own pace.
- Grade 4: Stops after walking 100m, or for a few minutes, on the level.
- Grade 5: Too breathless to leave the house.

For participants who perceive themselves to be in a Grade 5 on the traditional MRCD scale, the eMRCD will categorise them as either 5a or 5b depending on their ability to manage personal care (i.e. washing and dressing) (Nerys, W.,2017; Steer J. et al, 2011).

The baseline value used in analysis should be the stable state value captured at baseline post randomisation, the actually value taken at baseline during the exacerbated state is for describing baseline characteristics only.

- Health Status
 - St George's Respiratory Questionnaire (SGRQ)
 - COPD Assessment Tool (CAT)

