6.2 Demographic and Baseline Characteristics

Demographics, baseline characteristics and medical history will be summarised by treatment group and overall. This will include the summary of the stratification factors: baseline eMRC dyspnoea stable state (≤ 3 , > 3) and number of past hospitalisations in the previous 12 months (0, ≥ 1).

Numbers (with percentages) for binary and categorical variables, and means (with standard deviations) where data meets the normality assumptions or medians (with lower and upper quartiles) if otherwise will be presented. Where data is log transformed improve normality and allow for parametric testing the geometric mean on the original scale (i.e. after anti-logging the calculation of the mean on the log scale) must be presented alongside standard deviations on the log scale.

There will be no tests of statistical significance nor confidence intervals for differences between randomised groups on any baseline variable.

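### Time from randomisation to discharge becomes index-admission length of stay in the SAP's baseline table with no clear between-arm analysis, and the protocol's own definition fails for participants randomised after discharge

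*SAP*

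**What the plan says.** Protocol 3.3.2.1 includes "Time to discharge from randomisation" among the exacerbation and healthcare-utilisation outcomes. The endpoint table in Protocol 3.5 places it under the secondary objectives and describes it as "Time from randomisation to discharge, up to 48 weeks". Protocol 10.3.3 adds that "All time to event secondary outcomes will be analysed the same way as the primary outcome", which means a Cox model with the two stratification factors.

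SAP 3.2.1 keeps an item in this position in the list of secondary outcomes but defines it differently: "Time to discharge from index admission is a continuous outcome defined as the time (measured in days) from index admission to discharge". The resulting duration "will be incorporated into the baseline characteristics for analysis and reporting". On deaths it says: "Participants with a date of death and no discharge date will not have a value for length of index admission", and those participants are left out. The only output shell that names the item is a descriptive row of the demographic and baseline table in SAP Appendix 1. On such variables SAP 6.2 says: "There will be no tests of statistical significance nor confidence intervals for differences between randomised groups on any baseline variable". SAP 6.8, which is for changes to the planned analysis, records none.

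On timing, Protocol 7.2 says that "the participant can be consented at any point within their inpatient stay, or within one week of discharge". Randomisation follows consent.

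**The concern.** The two documents name different quantities, with different starting points and different roles. A statistician working from the SAP would produce a baseline row. A reader of the protocol would expect a comparison of arms. Protocol 7.11 commits the final report to the secondary outcomes of section 3.3.2, so the gap would show at reporting.

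The SAP quantity also serves neither role well. As a baseline variable it is wrong for anyone randomised while still in hospital, because its end point lies after allocation. As an outcome it carries days before randomisation that allocation cannot have affected. Leaving out those who die undischarged restricts the summary to participants who survived the index stay, which is itself a post-randomisation condition for those randomised as inpatients.

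**Working it through.** No figure is stated for this outcome, so the check is a comparison of texts and of dates.

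**1. The two definitions**

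| Feature | Protocol (3.3.2.1, 3.5, 10.3.3) | SAP (3.2.1, 6.2, Appendix 1) |
|---|---|---|
| Clock starts | Randomisation | Index admission |
| Type | Reads as time to event, though not labelled so | Continuous |
| Role | Secondary outcome | Listed as secondary, reported at baseline |
| Death before discharge | No specific rule | No value, left out |
| Comparison of arms | Cox model, if time to event | None clearly assigned |

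**2. What each clock measures.** Let A be the admission date, R randomisation and D discharge. The protocol quantity is D − R. The SAP quantity is D − A = (R − A) + (D − R).

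- *Inpatient at randomisation (R before D).* The SAP quantity is the pre-randomisation part, R − A, plus the protocol quantity, D − R. The first part cannot respond to allocation. The second lies after allocation, so the sum is not a baseline measure.
- *Randomised after discharge (R after D).* The SAP quantity lies wholly before randomisation. The protocol quantity D − R is negative. Protocol 8.4 requires the first injection within seven days of discharge for those not dosed in hospital, and randomisation precedes it, so D − R runs from 0 down to −7 days. Read as a time to event, it is undefined: the event occurred before the clock started.
- *Died in the index stay.* D does not exist. The SAP assigns no value. Participants who die after discharge keep theirs.

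**3. Is there a SAP method that fits?** SAP 6.5.1 has four: time to event, continuous longitudinal, count and categorical longitudinal. The SAP calls this outcome continuous, which takes it off the time-to-event route. It is measured once, so the repeated-measures model, with visit and baseline value as fixed effects, does not apply. It is neither a count nor categorical. None of the four fits.

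**4. Is the change declared?** SAP 6.8 declares nothing. The SAP does flag a departure elsewhere: SAP 6.4.1 says openly that the log-rank test in the protocol will not be presented. There is no such statement here.

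**5. Does anything carry over to the primary analysis?** No. The sample size in Protocol 10.1 uses only the 65% control event proportion, hazard ratio 0.6, 80% power and α = 0.05 (taken as two-sided), and it reproduces. Freedman's formula gives 126 events. The treated-arm proportion is 1 − (1 − 0.65)^0.6 = 0.467, the mean of the arms is 0.559, and 126 / 0.559 = 225.5, so 226. Then 226 / 0.95 = 237.9, so 238. Time to discharge does not enter.

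**The case against.** **The SAP may still intend a comparison.** It keeps the item under secondary outcomes and speaks of its analysis. SAP 6.5.1 sends all secondary outcomes other than adverse events to the modified intention-to-treat population. SAP section 5 gives a rank-sum comparison for non-normal continuous outcomes, and SAP 6.7 adjusts all secondary outcomes where the model allows. This stands in part. A reader might infer that no treatment estimate would be produced at all; the documents do not support that, because these generic sentences could be applied. But none names this outcome, the rank-sum text is written for repeated time points, and 6.2 rules out inference once the variable is baseline. Summaries by arm would appear in any case.

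**The protocol does not call it time to event.** This stands as a point of wording. In the endpoint table the other outcomes that run from randomisation carry that label and this row does not. Time to event is the natural reading, but it is not stated.

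**Describing the index stay at baseline is sensible.** With randomisation allowed after discharge, demoting the outcome to a description of the index admission could be defended, provided that it is declared and not labelled as pre-randomisation. It is not declared.

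**The harm is small and unmeasured.** The outcome is one of nine in its group and is not powered. The death rule touches only deaths after randomisation within the index stay; palliative patients are excluded and no count is given. In a descriptive row it biases no treatment estimate. A reader might also want to put a figure on the precision lost by including days before randomisation. The documents give no standard deviation of stay, no split around randomisation and no share randomised after discharge, so any such figure would be invented.

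**Conclusion.** The mismatch is established from the current text of both documents. A listed secondary outcome has been replaced, without declaration, by a different quantity reported in the baseline table. The SAP then gives conflicting signals on whether arms are compared and assigns no method that fits. For participants randomised as inpatients, the reported quantity is not a baseline variable. The protocol shares the fault: its definition does not work for participants randomised after discharge, so copying the protocol wording into the SAP would not be enough.

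The consequence is confined to this secondary outcome, and its numerical size cannot be given from the documents. The conclusion rests on the definitions and on the consent window, and on no assumption about lengths of stay, death rates or drug effect. It should be corrected before database lock but does not threaten the main result.

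**What to change.** Choose one of two routes and make both documents agree.

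**Keep the outcome.** In protocol and SAP, define it as days from randomisation to discharge alive among participants who are inpatients at randomisation. That status is fixed before allocation, so the restriction does not disturb the randomised comparison. Compare arms with a cause-specific Cox model including the two stratification factors, censoring at in-hospital death. Show cumulative incidence curves by arm, with in-hospital death as a competing event. State that a hazard ratio above 1 means faster discharge, the reverse of the primary outcome. Do not label full length of stay as baseline; if a baseline row is wanted, show days from admission to randomisation.

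**Remove the outcome.** Delete it from the secondary outcomes in both documents and record this, with the reason, in SAP 6.8. A descriptive row for length of stay could remain if it is marked as partly post-randomisation.

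The first route costs one extra model, one figure, a smaller analysis set and a matching protocol clarification. It needs no new data: the admission, randomisation, discharge and death dates already enter SAP derivations. Some inpatients may receive their first injection only after discharge (Protocol 8.4), so an effect of allocation on discharge could be small. The second route costs only wording, but gives up a listed outcome.

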The St George's Respiratory Questionnaire (SGRQ-C COPD specific) score is defined as a continuous outcome. There are two parts to the questionnaire providing a total of 3 component scores (or subscales) as below;

- Part 1: Symptoms (8 items).
- Part 2: Activity (16 items)
- Part 2: Impacts (26 items).

Each questionnaire response has a unique empirically derived 'weight'. The lowest possible weight is zero and the highest is 100. A Total and three component scores are calculated: Symptoms; Activity; Impacts.

The Symptoms component consists of all the questions in Part 1. The weights for Questions 1-7 are summed.

The Activity component is calculated from the summed weights for the positive responses to items Questions 9 and 12 in Part 2 of the questionnaire.

The Impacts component is calculated from Questions 8, 10, 11, 13, 14 in Part 2 of the questionnaire.

Then the Total score is calculated by summing the weights to all the positive responses in each component.

For each subscale and the total score, values range from 0 (no impairment) to 100 (maximum impairment) (Ferrer M. et al, 2002).

The COPD Assessment Tool (CAT) score is defined as a continuous outcome that ranges from 0 to 40 (inclusive) higher scores indicating a more severe health status impairment or a poorer control of COPD. It consists of eight items, with each item presented as a 6-point (0 to 5) differential scale, providing a score out of 40 indicating the clinical impact of the disease.

- Mental wellbeing
 - Warwick-Edinburgh Mental wellbeing score (WEMWBS)

The Warwick-Edinburgh Mental wellbeing score is defined as a continuous outcome that ranges from 14 to 70 (inclusive). The Questionnaire consists of 14 items with each item using a 5-point Likert scale: 1 ("None of the time"), 2 ("Rarely"), 3 ("Some of the time"), 4 ("Often") and 5 ("All of the time"). The total score sums all 14 items with higher scores indicating a higher level of mental wellbeing (Tennant R. et al, 2007).

- Functional
 - London Chest Activities of Daily Living Questionnaire (LCADL)

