6.5.3 Sensitivity Analyses

The primary analyses for all none time event outcomes (i.e continuous, binary and count outcomes) will consider any missing data to be missing at random (MAR) and complete case analysis carried out. However, if comparison of patterns of missingness and descriptive differences between treatment arms indicate this assumption is not valid, additional sensitivity analyses may be carried out and methods of imputation will be included in detail in the statistical analysis plan.

To ensure the reliability of the analysis of key secondary outcome measures, we will conduct a sensitivity analysis under various scenarios. This will involve evaluating the secondary outcomes; number of readmissions, number of exacerbations, and SGRQ (assessed for three sub-domains and the total score), to thoroughly assess the robustness of our results.

Individuals will be considered to have had some missing data for the two count variables if they have less than 47 weeks (48 weeks – 7day window) follow-up with the exception of those with planned truncated follow-up.

In the first approach, regardless of whether missingness is assumed to be random or non-random, we will perform the outlined statistical procedures. Additionally, we will provide descriptive characteristics of the missing group compared to the non-missing group, exploring potential similarities or dissimilarities between them. This comprehensive approach allows for a thorough examination of the impact of missing data on our study outcomes.

In the second approach, we are aware that throughout the trial, some participants may leave the study due to a high number of exacerbations or death before reaching their 48-week follow-up. This leads to missing data that is not at random, rendering

standard imputation methods inappropriate. Therefore, the data for key secondary outcomes for these participants will be analysed in the following way:

Pattern Mixture Model:

Robustness of the results will be assessed within the pattern mixture model. A pattern mixture model is a type of statistical model used to analyse data with missing values, especially when the missingness is not at random (MNAR).

This method is a 2-stage procedure where the 1st stage involves the use of multiple imputation to impute all missing values assuming data are “missing at random”.

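### The SAP's SGRQ scoring rule sums response weights without dividing by the maximum, so it cannot give the 0–100 range stated for every subscale and the Total

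*SAP*

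**What the plan says.** The scoring text is in SAP 3.2.1, Definition and Derivation of Secondary Outcomes.

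- **Instrument:** "The St George's Respiratory Questionnaire (SGRQ-C COPD specific) score is defined as a continuous outcome". Protocol 3.3.2.2 and 3.5 name only the SGRQ, as does the visit schedule in SAP 2.3.
- **Response weights:** "The lowest possible weight is zero and the highest is 100".
- **Item counts:** 8 for Symptoms, 16 for Activity and 26 for Impacts.
- **Symptoms:** "The weights for Questions 1-7 are summed".
- **Activity:** summed weights of the positive responses to Questions 9 and 12.
- **Impacts:** calculated from Questions 8, 10, 11, 13 and 14. The operation is not stated.
- **Total:** "Then the Total score is calculated by summing the weights to all the positive responses in each component".
- **Range:** "For each subscale and the total score, values range from 0 (no impairment) to 100 (maximum impairment".

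SAP 6.5.1.2 analyses continuous longitudinal outcomes with a mixed model and reports adjusted mean changes and mean differences with 95% confidence intervals. SAP 6.5.3 counts the SGRQ among the key secondary outcomes for sensitivity analysis: "number of readmissions, number of exacerbations, and SGRQ (assessed for three sub-domains and the total score".

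**The concern.** The section is headed as a derivation, so a programmer may fairly implement what it says. What it says is a sum. A sum of many weights, each of which may be as high as 100, is not confined to 0–100 unless it is divided by its own maximum, and that step is missing. No scoring manual is cited. The one reference at that point is a paper on interpreting SGRQ scores.

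At stake is the reported scale of a key secondary outcome that is analysed four ways (three components and the Total). Taken literally, the rule gives mean differences in raw weight units. These could not be read against the range the SAP states, and the components could not be compared with one another.

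**Working it through.** **Inputs (all from SAP 3.2.1).** Weight per response 0 to 100; items 8, 16 and 26; plain sums for Symptoms, Activity and the Total; stated range 0–100 for all four scores.

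**1. Do the neighbouring summed scores reproduce their stated ranges?**

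- CAT: 8 items × 5 = 40. Stated maximum 40.
- WEMWBS: 14 × 1 = 14 and 14 × 5 = 70. Stated range 14 to 70.
- LCADL: 15 × 5 = 75. Stated maximum 75.

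All three agree. In this section a stated sum is meant to produce the stated range.

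**2. Does the SGRQ rule?** Suppose each subscale is a sum with maximum 100, as stated. The Total sums the same weights, so its maximum is

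100 + 100 + 100 = 300, against a stated 100.

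No knowledge of the weights is needed. The result also does not depend on how Impacts is formed: Symptoms and Activity, which are expressly summed, already contribute 100 + 100 = 200, and no weight is negative. The stated range is not reproduced.

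**3. What would the weights have to be?** A plain sum over n items has maximum n × (mean top weight), so a maximum of 100 needs a mean top weight of 100 / n:

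| Score | n | Mean top weight needed |
|---|---|---|
| Symptoms | 8 | 12.5 |
| Activity | 16 | 6.25 |
| Impacts | 26 | 3.85 |
| Total | 50 | 2.0 |

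These cannot hold together. The first three rows imply a mean of 300 / 50 = 6.0 over all items, not 2.0.

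**4. How large could the raw sums be?** The weights are not in the documents, so the mean top weight is an assumption. Summing is also assumed for Impacts.

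| Assumed mean top weight | Symptoms (8) | Activity (16) | Impacts (26) | Total (50) |
|---|---|---|---|---|
| 25 | 200 | 400 | 650 | 1250 |
| 50 | 400 | 800 | 1300 | 2500 |
| 75 | 600 | 1200 | 1950 | 3750 |
| 100 (upper bound) | 800 | 1600 | 2600 | 5000 |

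Within a row the components stand in the ratio 8 : 16 : 26, so equal relative impairment gives different raw scores. The table shows a range of possibilities and does not estimate the actual distortion.

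**5. With the missing step.** Score = 100 × (sum of endorsed weights) / (maximum possible sum over the same items). At maximum impairment the two sums are equal, so the score is 100 for each component and for the Total, whatever the weights. Numerator and denominator must cover the same items: with equal top weights, summing 7 items over an 8-item maximum would cap Symptoms at 100 × 7 / 8 = 87.5.

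**6. Effect on inference.** Dividing outcome and baseline by a constant c divides the mean difference, its standard error and both confidence limits by c. The test statistic and p-value for that score do not change. The rank-based fallback in SAP 6.5.1.2 is also unaffected.

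**The case against.** The best defence is that this is an omitted line and not a decision to report raw sums. The SAP states the required output range, so a range check would probably expose a program without the divisor, and a statistician who knows the instrument would add it. No SGRQ threshold or responder analysis is planned, and p-values are unaffected. All of that stands, and it limits the harm to scale and interpretability. It does not make the written rule correct: the plan states an operation that fails to give its own stated result, and the correction has to come from outside both documents.

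Several stronger readings are tempting but are not supported:

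- **That the item counts contradict the question list.** The SAP has "Part 1: Symptoms (8 items" and scores Questions 1–7. But it counts items and numbered questions separately (16 Activity items in 2 questions, 26 Impacts items in 5), so one Symptoms question may hold two items. The mapping needs stating; no error is shown.
- **That the wrong version is being scored.** SGRQ-C in the SAP may simply be more specific than SGRQ in the protocol. Nothing shows that a different version was administered.
- **That the error is tenfold, or that two positive responses take a score past 100.** Both need individual weights, which the documents do not list.
- **That SGRQ is the main health-status endpoint.** Protocol 3.3.2.2 lists SGRQ and CAT side by side under health status.

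**Conclusion.** The point holds for the scoring rule. As written, the rule cannot give 0–100 for all three subscales and the Total. The size that can be shown from the documents alone is a Total with maximum 300 against a stated 100, if the subscale ranges are taken as true. This rests on reading 100 as the score at maximum impairment, as the SAP puts it, and on the Total summing the same weights as the components. Impacts is not expressly summed, but the contradiction does not need it to be.

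The consequence is limited to the units of SGRQ means, mean differences and confidence intervals. A reader might infer that the test of treatment on SGRQ is compromised. It is not, provided the divisor is fixed. That proviso matters only for incomplete questionnaires, for which neither document gives an item-level rule. The primary outcome and the sample size do not use the SGRQ.

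**What to change.** In SAP 3.2.1, replace the scoring sentences with a single rule: score = 100 × (sum of weights for endorsed responses) / (maximum possible sum of weights over the same items). Apply it separately to Symptoms, Activity and Impacts, and to the Total over all items. This also supplies the operation that is missing for Impacts.

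In the same edit:

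- State how the 8 Symptoms items map to Questions 1–7, so that numerator and denominator cover the same items.
- Name the version administered, SGRQ or SGRQ-C, in the same way in Protocol 3.3.2.2 and 3.5 and in the SAP, and refer to that version's weights.
- Say how unanswered items are treated, since this determines whether the divisor is fixed.

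The cost is a few lines of SAP text, a naming correction in the protocol if one is needed, and a check of the scoring program. No new data are required.
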